5.5.6 Recommendations for the treatment of MS relapses

MS relapses may be treated with a standard short course of corticosteroids (e.g. methylprednisolone) on an inpatient or outpatient basis. Steroid treatment should consist of 3-5 days and up to 1,000 mg methylprednisolone/day or equivalent. The decision to treat should be based on Investigator's judgment and/or local clinical practice. Standard of care will be followed during treatment.

Taper with oral steroids is not permitted.

Investigators should consider the added immunosuppressive effects of corticosteroid therapy and increase vigilance regarding infections during such treatment and in the weeks following administration.

Use of steroids for treatment of relapse must be recorded on the appropriate eCRF.

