5.5.7 Concomitant medication

The Investigator must instruct the patient to notify the study site about any new medications he/she takes after the patient was enrolled into the study. All medications (including dose changes), procedures and significant non-drug therapies (including physical therapy and blood transfusions) administered after the patient was enrolled into the study must be recorded in the appropriate CRF.

Each concomitant drug must be individually assessed against all exclusion criteria/prohibited medication. If in doubt the Investigator should contact the Sponsor before randomizing a patient or allowing a new medication to be started.

Premedication prior to sc injection

Premedication with acetaminophen and/or antihistamines (or equivalent) is recommended and may be administered at the discretion of the Investigator. Only for the first injection of Double-blind treatment period (Day 1) and Double-blind loading dose period (Week 24), the addition of premedication with steroids (methylprednisolone 100 mg iv or equivalent) is recommended. Premedication should be administered 30 to 60 min prior to study drug injection.

Any administration of premedication must be recorded in the appropriate CRF.

Additional information in regards to premedication for home-administration use:

From Week 25 onwards, patients may inject study medication at home (refer to [Section 5.5.4](#)). Use of premedication is at the discretion of the Investigator. Based on the experience with the injections administered at the site and with the use of any premedication, the Investigator will evaluate whether or not premedication (such as acetaminophen and/or antihistamines) should be used before injections administered at home. If premedication is prescribed, the study staff

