13. In case of relapse, if an MRI for efficacy has been scheduled within 14 days of the initiation of steroid treatment, the MRI should be performed before steroid treatment is initiated. No MRI for efficacy should be performed while a patient is on steroid therapy for relapse and within 14 days upon termination of steroid therapy.
14. MRI scan at the EOS is needed if there was no MRI scan in the last 3 months.
15. Including corticosteroids used to treat MS relapse; any newly started MS treatment as applicable (for patients who have discontinued study medications).

16. Applicable for patients who take study treatment by home-administration. Telephone interview by site staff should take place around time of the sc self/home injection to query about any new or worsening symptoms warranting an unplanned visit, injection reactions, results of home pregnancy testing, compliance with contraception requirements as applicable.
17. Patients will receive sc injections of Double-blind treatment period on Day 1, Day 7 (\pm 1 day), Day 14 (\pm 1 day), Week 4 (\pm 3 days), Week 8 (\pm 3 days), Week 12 (\pm 3 days), Week 16 (\pm 3 days) and Week 20 (\pm 3 days), the sc injection of the Double-blind loading dose period at Week 24 (\pm 3 days), Week 25 (\pm 1 day) and Week 26 (\pm 1 day), and the Open-label ofatumumab sc injection from Week 28 (\pm 3 days), followed by every 4 weeks (\pm 3 days).
18. Labs must be drawn to allow adequate time for results to be obtained before randomization to ensure patient's eligibility
19. Patients do not have to visit the site at Week 25 and 26 if they are permitted to administer the sc injection at home at investigator's discretion.
20. If the trial is extended beyond Week 72, every 12 weeks visit (Week 84, 96 and so forth) will be performed with same measurements as at Week 60, 72 and so forth.

[REDACTED]

[REDACTED]

Table 6-2 Assessment schedule for Safety Follow-up period

Visit Week ¹ (relative to EOS)	+W12	+W24	+W36	Every 12 weeks ²	End of Safety-FU ³
Visit Number	410	420	430	440/4XX	2999
Visit window (days)	±14	±14	±14	±14	
AEs	X	X	X	X	X
Concomitant Meds*	X	X	X	X	X
Vital Signs	X	X	X	X	X
eCSSRS	X	X	X	X	X
Urine pregnancy test ⁴	X	X	X	X	X
Contraception status	X	X	X	X	X
Laboratory sample including sample for B-cells and T-cells	X	X	X	X	X
Sample for Total IgG, IgM	X	X	X	X	X
MS Relapse	X	X	X	X	X
EDSS	X	X	X	X	X

W=week.

1. Time measured from the EOS visit.

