6.4.3 Magnetic Resonance Imaging (MRI)

All patients will undergo MRI scanning of the brain according to the schedules in [Table 6-1](#).

MRI scans will be read by the central MRI reading center. The central reading center will be blinded with no access to information on treatment assignments. Prior to the start of the study, MRI technician from each center will receive an MRI Manual, outlining technical implementation, image quality requirements and MRI administrative procedures. Each site will be asked to program the MRI scanner that is designated for evaluation of the study patients and perform and submit a dummy scan (so called “dummy or dry run”) to the MRI reading center to assess the image quality and to evaluate the compatibility of the electronic data carrier. Once the dummy run has been accepted, all the parameter settings for the study specific MRI sequences must remain unchanged for the duration of the study.

Each MRI scan performed for the study needs to be previewed by a local radiologist/neurologist. The Investigator will review the MRI performed during the Screening period to assess patient's eligibility. After Randomization, the Investigator will be contacted in case of unexpected or safety-related findings detected on the MRI scan. The investigator may review the MRI scans from Week 36 onwards, regardless of safety concerns.

During the study, the quality of each scan performed will be assessed by the central blinded MRI reading center. The MRI scan should be sent to the central MRI reading center upon completion. As soon as the scan is received by the central MRI reading center, it will be evaluated for quality, completeness and adherence to the protocol. Confirmation of MRI quality or a description of the quality problems, if detected, will be communicated to the site. If scan is incomplete or incorrectly performed, the study center will be asked to repeat it as soon as possible. After completion of the quality check, all scans will be analyzed according to the MRI protocol.

Restrictions for MRI schedule

To avoid interferences caused by steroids (in regards to Gd-enhancing lesions) for the treatment of MS relapse, the following restrictions apply for this study:

- In case of relapse, if an MRI has been scheduled within 14 days of the initiation of steroid treatment, MRI (with Gd-enhancement) should be performed **before** steroid treatment is initiated.

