- No MRI (with Gd-enhancement) should be performed while a patient is on steroid therapy for relapse and within the following 14 days upon termination of steroid therapy.

[figure not shown]
As a result of these restrictions, MRI scheduling can be adjusted accordingly. In case a visit is performed outside the visit window, any subsequent visits should be performed according to the original visit schedule.

Scanning

All sequences/scans will be performed according to the institute MRI manual.

Sequences include T1 hypointense images (with and without contrast medium, gadolinium-DTPA), T2-weighted images and brain volume will be performed.

The contrast medium may occasionally cause nausea and vomiting. Allergic reactions may also occur very rarely and, in extremely rare instances, can be potentially serious and require immediate anti-anaphylactic treatment.

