2.1.2.1 Visit windows during core and extension treatment periods

Table 2-1 Visit windows for MRI

Visit-window	Start day	Target day	End day
Week 12	1	84	98
Week 16	99	112	126
Week 20	127	140	154
Week 24 (Cut-off 1)	155	168	182
Week 36	183	252	294
Week 48	295	336	378

Day counts are relative to the first date of study drug in the Core part.

Table 2-2 Visit windows for [REDACTED] EDSS

Visit-window	Start day	Target day	End day
Week 12	1	84	126
Week 24 (Cut-off 1)	127	168	210
Week 36	211	252	294
Week 48	295	336	378
Week 60	379	420	462

Visit-window	Start day	Target day	End day
Week 72	463	504	546
Week x*	x*7-42+1	x*7	x*7+42

*if study goes beyond Week 72, every 12 weeks the same assessments on Week 60 and Week 72 will be performed. X will be a multiple of 12 weeks from Week 84 and beyond.
Day counts are relative to the first date of study drug in the Core part.

Table 2-3 Visit windows for routine lab (including urine), ADA, and Total IgM, IgG levels

Visit-window	Start day	Target day	End day
Week 4	1	28	56
Week 12	57	84	126
Week 24 (Cut-off 1)	127	168	182
Week 28	183	196	224
Week 36	225	252	294
Week 48	295	336	378
Week 60	379	420	462
Week 72	463	504	546
Week x*	x*7-42+1	x*7	x*7+42

*if study goes beyond Week 72, every 12 weeks the same assessments on Week 60 and Week 72 will be performed. X will be a multiple of 12 weeks from Week 84 and beyond.
Day counts are relative to the first date of study drug in the Core part for Cut-off 1 analysis, or the first date of ofatumumab for Cut-off 2 and final analysis.

[figure not shown]

Table 2-5 Visit windows for B-cell counts and T-cell counts: Cut-off 1 analysis

Visit-window	Start day	Target day	End day
Day 2	--	2	--
Day 5	3	5	--
Day 7	6	7	10
Day 14	11	14	21

Visit-window	Start day	Target day	End day
Week 4	22	28	56
Week 12	57	84	126
Week 24 (Cut-off 1)	127	168	182

Day counts are relative to the first date of study drug in the Core part.

Table 2-6 Visit windows for B-cell and T-cell counts: Cut-off 2 and final analysis

Visit-window	Start day	Target day	End day
Week 4	1	28	56
Week 12	57	84	126
Week 24	127	168	210
Week 36	211	252	294
Week 48	295	336	378
Week 60	379	420	462
Week 72	463	504	546
Week x*	$x * 7 - 42 + 1$	$x * 7$	$x * 7 + 42$

*if study goes beyond Week 72, every 12 weeks the same assessments on Week 60 and Week 72 will be performed. X will be a multiple of 12 weeks from Week 84 and beyond.

Day counts are relative to the first date of ofatumumab.

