2.5.2 Statistical hypothesis, model, and method of analysis

The null hypothesis is that there is no difference in the number of Gd-enhanced T1 lesions per scan between ofatumumab and placebo during the Core part (Cut-off 1 analysis). The alternative hypothesis is that there is a difference between the 2 treatment groups.

- Superiority of ofatumumab over placebo will be concluded if the mean number of Gd-enhanced T1 lesions per scan in patients treated with ofatumumab is lower compared with placebo and the observed p-value for the between-treatment comparison is less than the two-sided significance level of 0.05.

The null hypothesis will be tested on the FAS using a negative binomial regression model with log-link. Each patient's total number of Gd-enhanced T1 lesions during the Core part will be used as the response variable, and natural log of the number of MRI scans will serve as the offset variable to adjust for the different number of MRI scans between patients. The model will include treatment, region (Japan or other countries), and baseline number of Gd-enhanced T1 lesions (0 or ≥ 1) as factors.

The number of Gd-enhanced T1 lesions per scan will be estimated by treatment with 95% confidence interval. The between treatment effect will be calculated as rate-ratio (ofatumumab/placebo) with 95% confidence interval and p-value will be provided. In addition, the relative reduction in the number of Gd-enhanced T1 lesions per scan will be computed as one (1) minus the rate-ratio and expressed as a percentage.

The number of Gd-enhanced T1 lesions will be summarized descriptively by visit-window and treatment group.

Analyses on Gd-enhanced lesions will exclude MRI evaluation performed within 14 days after termination of systemic corticosteroids and/or adrenocorticotrophic hormone.

The above summary analyses will be repeated with additional data from the extension part at the Cut-off 2 analysis ([Section 2.14](#)).

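### The SAP drops Gd scans taken in the 14 days after a steroid course but not those taken during it; the effect is very small and one change of wording closes the gap

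*SAP*

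**What the plan says.** The primary analysis (SAP 2.5.2) is a negative binomial regression of each patient's total Gd-enhanced T1 lesions in the Core part, with the log of the number of scans as offset. The scans are those at Weeks 12, 16, 20 and 24 (SAP 2.5.1). On steroid-affected scans SAP 2.5.2 says: "Analyses on Gd-enhanced lesions will exclude MRI evaluation performed within 14 days after termination of systemic corticosteroids and/or adrenocorticotrophic hormone".

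Protocol 6.4.3 gives steroid interference with Gd-enhancing lesions as the reason for restricting scans. It says "No MRI (with Gd-enhancement) should be performed while a patient is on steroid therapy for relapse" and extends the bar to the 14 days after therapy ends. Footnote 13 of Table 6-1 repeats both intervals: "No MRI for efficacy should be performed while a patient is on steroid therapy for relapse and within 14 days upon termination". Protocol 6.4.3 also directs that a scan falling due within 14 days of starting relapse steroids be done before the steroids, and it allows scan dates to be moved. On the length of a course, Protocol 5.5.6 says: "Steroid treatment should consist of 3-5 days and up to 1,000 mg methylprednisolone/day or equivalent".

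**The concern.** The SAP rule is the analysis-side safeguard for a scan that breaks the protocol's bar, so it should cover the same two intervals. Read literally, it covers one. A scan on day 3 of a 5-day course is not a scan after the course has ended, so its lesions and its unit of offset are both kept. Such a scan is as exposed to steroid suppression as one taken shortly afterwards, which is dropped.

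At stake are the accuracy and reproducibility of the primary endpoint. Two programmers, one following the SAP and one following the protocol, could include different scans. On the planning relapse rates, relapse steroids would be used more often per patient on placebo. Any retained on-steroid scans would then lower the placebo count proportionally more and pull the rate ratio towards 1.

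**Working it through.** **1. The plan's own power figure.** Inputs (Protocol 9.9, SAP 3): 60 patients randomized 2:1, so 20 placebo and 40 ofatumumab; 1.0 and 0.08 lesions per scan; dispersion 4.5; one-sided 0.025, which has the same critical value as two-sided 0.05; 10% dropout. With t = 4 scans and a Wald test on the log rate ratio:

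- Variance = (1/(1.0 × 4) + 4.5)/20 + (1/(0.08 × 4) + 4.5)/40 = 0.2375 + 0.1906 = 0.4281; SE = 0.654.
- Power = Φ(2.526/0.654 − 1.960) = Φ(1.900) = 97.1%.
- With 18 and 36 patients (10% dropout): 95.6%.

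Other choices of null variance give up to 98.1% and 97.0%. All agree with the stated figure of more than 90%.

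**2. The two rules side by side.**

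| Scan taken | Protocol 6.4.3, Table 6-1 fn 13 | SAP 2.5.2 |
|---|---|---|
| Day 3 of a 5-day relapse course | barred | kept |
| 10 days after the course ends | barred | excluded |
| Before the first steroid dose | allowed | kept |

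No other text fills the first row. Protocol 9.4.2 and 9.4.3 and SAP 5.5.1 contain no scan-exclusion rule. In SAP Table 5-4, the on-treatment deviation that mentions corticosteroids (COMD03) concerns chronic use. It also removes patients from the per-protocol set rather than scans from the primary analysis.

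**3. How many scans could be affected.** Inputs: planning relapse rates of 0.4 and 0.16 per year (Protocol 9.9.2, SAP 3.2); courses of 3-5 days (Protocol 5.5.6); 20 × 4 = 80 placebo scans and 40 × 4 = 160 ofatumumab scans. Assumptions: every relapse is treated, scan timing is unrelated to relapse, and the protocol bar is ignored.

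Expected scans inside a course = scans × relapse rate × course days / 365.25.

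- Placebo: 80 × 0.4 × 3/365.25 = 0.26, to 80 × 0.4 × 5/365.25 = 0.44.
- Ofatumumab: 160 × 0.16 × 3/365.25 = 0.21, to 160 × 0.16 × 5/365.25 = 0.35.
- Total: 0.47-0.79 of 240 scans, or 0.20%-0.33%.

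For comparison, the 14-day interval that the SAP does cover would hold 80 × 0.4 × 14/365.25 + 160 × 0.16 × 14/365.25 = 1.23 + 0.98 = 2.2 scans on the same assumptions.

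**4. Effect if those scans stay in and all read zero.** The probability that a scan falls inside a course is 0.0033-0.0055 on placebo and 0.0013-0.0022 on ofatumumab.

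- 3-day courses: 0.08 × (1 − 0.00131)/(1 − 0.00329) = 0.0802.
- 5-day courses: 0.08 × (1 − 0.00219)/(1 − 0.00548) = 0.0803.
- Power: 97.1% (n = 60) or 95.5% (n = 54).

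If instead exactly one placebo scan were affected, and it would otherwise have shown the planning mean of 1.0 lesion, the rate ratio would be 0.08 × 80/79 = 0.0810.

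**5. Effect of excluding them.** Power is 97.1% (n = 60) or 95.6% (n = 54), the same to one decimal as in step 1.

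**The case against.** The strongest reply is that an on-steroid scan can exist only if a site breaks an explicit instruction. The protocol directs the scan before steroids start, bars it during therapy and lets it be moved. Even then the expected number is below one in 240, and the bias runs against the sponsor's claim. All of that stands, and it makes this a minor point. It does not answer the wording gap. The SAP rule already exists to handle the same kind of breach in the following 14 days, and it omits the days on therapy.

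A reader might go further and infer that the rule mishandles the Week 24 scan, because it covers any systemic corticosteroid and at Week 24 "the addition of premedication with steroids (methylprednisolone 100 mg iv or equivalent) is recommended". The documents do not support that.

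- Core assessments must be completed before the Week 24 dose (Protocol 6; Table 6-1 footnote 4), and premedication is given 30 to 60 minutes before the injection. A scan done before the premedication does not follow a steroid and is kept on a plain reading. The SAP does not prescribe a date-only comparison. If a program did delete every Week 24 scan, power with three scans would still be 96.2% (n = 60) or 94.3% (n = 54).
- A reader might also expect a repeat scan ("If scan is incomplete or incorrectly performed, the study center will be asked to repeat it as soon as possible") to enter the primary count after a placebo patient has started ofatumumab, since the Week 24 window in SAP Table 2-1 runs to Day 182. But the response is restricted to the Core part, and the Extension starts with the Week 24 injection (SAP 1.1). The windows serve by-visit summaries, and unscheduled visits are not mapped to them for efficacy (SAP 2.1.2). No turnaround time is given that would place repeats after the injection as a rule.

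What remains for Week 24 is an unstated convention: how a scan and a steroid dose on the same calendar date are ordered.

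**Conclusion.** The SAP exclusion is narrower than the protocol's scan restriction. Followed literally, it would keep a scan taken during a steroid course in both the lesion total and the offset. This is a genuine but minor misalignment, worth correcting for accuracy and reproducibility rather than for power.

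The size is an upper bound of 0.26-0.44 placebo scans out of 80, a rate ratio of 0.0802-0.0803 instead of 0.0800, and power of about 97% either way. This rests on the planning relapse rates, treatment of every relapse, no rescheduling, and scan timing and lesion load unrelated to relapse. If scans at relapse would have carried more lesions than average, the shift would be larger, but on the same small expected number of scans. The bias is conservative as long as relapses are more frequent per patient on placebo.

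A reader might infer a larger effect by taking all placebo relapses over 24 weeks (20 × 0.4 × 168/365.25 = 3.68) and multiplying by 3/28 to 5/28, which gives 0.39-0.66 scans. That is too high by 168/112 = 1.5, because the primary endpoint uses four scans from Week 12 onwards and earlier relapse courses cannot coincide with them. Nor do the documents support a reading that the primary result is materially biased.

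**What to change.** Reword the sentence in SAP 2.5.2 along these lines:

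*Gd analyses exclude any scan performed after the first dose of a systemic corticosteroid/ACTH course through 14 days after its last dose; a scan on the same date as the first steroid dose (including Week 24 premedication) is treated as pre-dose unless recorded times show otherwise.*

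Starting the exclusion after the first dose, rather than on the first day, protects the pre-steroid scan that Protocol 6.4.3 asks for when both fall on one date. The same-date default is needed because the documents do not show that scan and premedication clock times are collected.

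As an optional clarification only, state that scans after the Week 24 injection are not Core data for the Cut-off 1 analysis.

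The cost is SAP wording and one programming condition. Relapse steroids and premedication are already recorded on the CRF (Protocol 5.5.6 and 5.5.7). The downside is possibly one fewer scan in the offset. If the Cut-off 1 analysis has already been run, the equivalent step is to check whether any included scan fell inside a steroid course and to report the answer.

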2.5.3 Handling of missing values/censoring/discontinuations

The primary negative binomial model with an offset for the number of MRI scans adjusts for missing information (dropout) under the assumption of non-informative dropout, information missing at random, and constant number of Gd-enhancing T1 lesions per scan within patient. Missing values will not be imputed. However, deviations from assumptions will be tested in sensitivity analyses.

2.5.4 Supportive analyses

Sensitivity analysis

The primary analysis will be repeated using the per-protocol set to provide an analysis of on-treatment data from subjects who have no major protocol violations. The analysis will be performed for Cut-off 1 analysis.

Additional sensitivity analyses may be defined in the analysis plan prior to database lock.

Consistency across regions

Consistency in efficacy across regions on the primary variable will be evaluated using a statistical model similar to the primary model, but with a treatment-by-region (Japan or other countries) interaction term added. The mean number of Gd-enhancing T1 weighted MRI lesions per scan will be provided by treatment and region. The rate-ratio will be presented for individual regions separately, together with 95% confidence intervals. The p-value of the treatment-by-region interaction will be displayed.

The estimates for individual regions will be displayed via a forest plot to visualize consistency.

The consistency across regions will be examined at Cut-off 1 analysis.

2.6 Analysis of the key secondary objective

There are no key secondary objectives.

2.7 Analysis of secondary efficacy objective(s)

All efficacy analyses will be done based on the FAS, unless explicitly stated otherwise.

2.7.1 Secondary endpoints

The secondary efficacy endpoints are:

Core part:

- Number of new or enlarging T2 lesions on MRI scans;
- Annualized relapse rate (ARR);
- Time to first relapse
- MS relapse characteristics

Extension part, including Core part: assess extended efficacy of ofatumumab in

- Number of Gd-enhanced T1 lesions
- Number of new or enlarging T2 lesions
- Annualized relapse rate (ARR)
- Time to first relapse
- MS relapse characteristics

